## AMENDMENT HISTORY

This is the original version. No amendment history.

**ABBREVIATIONS AND DEFINITION OF TERMS**

Abbreviation	Explanation
ALP	Alkaline Phosphatase
ALT	Alanine Transaminase
AST	Aspartate Transaminase
ATC	Anatomical Therapeutic Chemical
B.I.D.	Twice a Day
BLQ	Below Limit of Quantification
BMI	Body Mass Index
CI	Confidence Intervals
CMH	Cochran-Mantel-Haenszel
CSR	Clinical Study Report
CTCAE	Common Terminology Criteria for Adverse Events
CV	Coefficient Of Variation
DSMB	Data Safety Monitoring Board
ECG	Electrocardiogram
eCRF	Electronic Case Report Form
EOT	End Of Treatment
FAS	Full Analysis Set
HRQoL	Health-Related Quality of Life
hs-CRP	High-Sensitivity C-Reactive Protein
IBDQ	Inflammatory Bowel Disease Questionnaire
IRT	Interactive Response Technology
LLOQ	Lower Limit of Quantification
MedDRA	Medical Dictionary for Regulatory Activities
MES	Mayo Endoscopic Score
MCS	Full Mayo Clinic Score
mMCS	Modified Mayo Clinic Score
mRNA	Messenger Ribonucleic Acid
NI	Nancy Histopathology Index
P.O.	By Mouth
PD	Pharmacodynamic(S)
PGA	Physician's Global Assessment

Abbreviation	Explanation
PK	Pharmacokinetic(S)
PP	Per-Protocol
PT	Preferred Term
Q.D.	Once A Day
Q.D.-E	One A Day (Evening)
Q.D.-M	Once A Day (Morning).
QTcF	QT Interval Corrected Through Use of Fridericia's Formula
RHI	Robarts Histopathology Index
SAE	Serious Adverse Event
SD	Standard Deviation
SFU	Safety Follow-Up
SOC	System Organ Class
TEAE	Treatment Emergent Adverse Event
UC	Ulcerative Colitis
ULN	Upper Limit of Normal
WHODD	World Health Organization Drug Dictionary

## 1. INTRODUCTION

This statistical analysis plan (SAP) is designed to outline the statistical analysis methods in evaluating the efficacy and safety of study drug MORF-057 in adult participants with moderately to severely active ulcerative colitis (UC) for Phase 2b study MORF-057-202: A Phase 2b, Randomized, Double-blind, Placebo-controlled Study to Evaluate the Safety and Efficacy of 3 Active Dose Regimens of MORF-057 in Adults with Moderately to Severely Active Ulcerative Colitis (EMERALD-2).

This document has been prepared based on the protocol dated 26Apr2023 and CRF dated 14Jun2024. Details will be described in this analysis plan to ensure summary of tables, figures and listings, and the statistical methodology that will be used, are complete and appropriate to allow valid conclusion regarding the study objectives.

### 1.1. Study Objectives and Endpoints

The following study objectives (Table 1) will be completed by assessing the associated endpoints in participants with moderately to severely active UC.

**Table 1: Study MORF-057-202 Objectives and Endpoints**

Objectives	Endpoints
Primary Efficacy	
To evaluate the effects of MORF-057 on clinical remission at Week 12	
 
Proportion of participants in clinical remission at Week 12 as determined using the Modified Mayo Clinic Score (mMCS). The mMCS is a composite of the following subscores: 
 
Mayo endoscopic subscore (MES)
 
Mayo Clinic Score (MCS) stool frequency subscore
 
MCS rectal bleeding subscore
 
 
 

Secondary Efficacy	
To evaluate the effects of MORF-057 on clinical response at Week 12	
 
Proportion of participants with clinical response at Week 12 as determined using the mMCS
 

Exploratory Efficacy	
 
•
 

To evaluate the effects of MORF-057 on clinical remission at Week 52	
 
Proportion of participants in clinical remission at Week 52 as determined using the mMCS
 

To evaluate the effects of MORF-057 on clinical response at Week 52	
 
Proportion of participants with clinical response at Week 52 as determined using the mMCS
 

To evaluate the effect of MORF-057 on MCS remission at Weeks 12 and 52	
 
Proportion of participants in MCS remission at Weeks 12 and 52. MCS is a composite of the following subscores: 
 
MES
 
MCS stool frequency subscore
 
MCS rectal bleeding subscore
 
MCS Physician's Global Assessment (PGA)
 
 
 

Objectives	Endpoints
To evaluate the effect of MORF-057 on MCS response at Weeks 12 and 52	
 
Proportion of participants with MCS response at Weeks 12 and 52
 

To evaluate the effects of MORF-057 on histologic remission at Weeks 12 and 52	
 
Proportion of participants in histologic remission at Weeks 12 and 52 as determined using the Robarts Histopathology Index (RHI) Score
 
Proportion of participants in histologic remission at Weeks 12 and 52 as determined using the Nancy Histopathology Index (NI)
 
Proportion of participants in histologic remission at Weeks 12 and 52 as determined using the Continuous Geboes Score
 

To evaluate the effects of MORF-057 on histologic improvement at Weeks 12 and 52	
 
Proportion of participants with histologic improvement at Weeks 12 and 52 as determined using the RHI
 

To evaluate the effect of MORF-057 on endoscopic improvement at Weeks 12 and 52	
 
Proportion of participants with endoscopic improvement at Weeks 12 and 52 as determined using the MES
 

To evaluate the effects of MORF-057 on endoscopic remission at Weeks 12 and 52	
 
Proportion of participants in endoscopic remission at Weeks 12 and 52 as determined using the MES
 

To evaluate the effects of MORF-057 on mucosal healing at Weeks 12 and 52	
 
Proportion of participants in endoscopic remission as determined using the MES and histologic remission as determined using the RHI at Weeks 12 and 52
 

To evaluate the effects of MORF-057 on mucosal improvement at Weeks 12 and 52	
 
Proportion of participants with endoscopic improvement as determined using the MES and a histologic improvement as determined using the RHI at Weeks 12 and 52
 

To evaluate the effects of MORF-057 on symptomatic response at Weeks 2 and 6	
 
Proportion of participants with symptomatic response at Weeks 2 and 6 as determined using the Partial mMCS. Partial mMCS is a composite of the following subscores: 
 
MCS stool frequency subscore
 
MCS rectal bleeding subscore
 
 
 

To evaluate the effects of MORF-057 on Partial MCS response at Week 6	
 
Proportion of participants with Partial MCS response at Week 6. Partial MCS is a composite of the following subscores: 
 
MCS stool frequency subscore
 
MCS rectal bleeding subscore
 
MCS PGA
 
 
 

To determine time to symptomatic response by Week 12	
 
Time to symptomatic response by Week 12 as determined using the Partial mMCS
 

Objectives	Endpoints
To assess the effect of MORF-057 on non-endoscopic biomarkers of inflammation at Weeks 12 and 52	
 
Change from baseline to Weeks 12 and 52 in high-sensitivity C-reactive protein (hs-CRP) levels
 
Change from baseline to Weeks 12 and 52 in fecal calprotectin levels
 

To evaluate the effect of MORF-057 on patient-reported outcomes (PROs) at Weeks 12 and 52	
 
Change from baseline to Weeks 12 and 52 in Inflammatory Bowel Disease Questionnaire (IBDQ) Score
 

To evaluate the effect of MORF-057 on corticosteroid-free remission at Week 52	
 
Proportion of participants in corticosteroid-free remission at Week 52, as determined using the mMCS, among the participants who were on a stable dose of corticosteroids at baseline
 

To characterize the effect of MORF-057 on the need for UC-related hospitalizations and surgeries	
 
Percentage of participants requiring UC-related hospitalization or surgery at Weeks 12 and 52
 

To evaluate the long-term histologic and endoscopic effects of MORF-057 at Week 104	
 
Proportion of participants in histologic remission at Week 104 as determined using the RHI
 
Proportion of participants in histologic remission at Week 104 as determined using the NI
 
Proportion of participants in histologic remission at Week 104 as determined using the Continuous Geboes Score
 
Proportion of participants with histologic improvement at Week 104 as determined using the RHI
 
Proportion of participants with endoscopic improvement at Week 104 as determined using the MES
 
Proportion of participants in endoscopic remission at Week 104 as determined using the MES
 
Proportion of participants in endoscopic remission as determined using the MES and histologic remission as determined using the RHI at Week 104
 
Proportion of participants with endoscopic improvement as determined using the MES and a histologic improvement as determined using the RHI at Week 104
 

Safety	
To assess the safety and tolerability of MORF-057	
 
Frequencies and proportions for TEAEs, treatment-emergent serious adverse events (TESAEs), and TEAEs leading to study drug discontinuation
 

Pharmacokinetics (PK)	

Objectives	Endpoints
To characterize the PK of MORF-057	
 
MORF-057 concentration in plasma
 

Exploratory Pharmacodynamics (PD)	
To characterize the PD of MORF-057 in peripheral blood	
 
<math>\alpha 4\beta 7</math> receptor occupancy in blood over time
 
<math>\alpha 4\beta 1</math> receptor occupancy in blood over time
 
Change from baseline over time in blood in CCR9 messenger ribonucleic acid (mRNA)
 
Change from baseline over time in blood lymphocyte subsets
 

The definitions of efficacy endpoints are described in the following table.

**Table 2: Efficacy Endpoints Definitions**

Term	Definition
Clinical remission	Determined using the mMCS: Rectal bleeding subscore of 0; a stool frequency subscore of $\leq 1$ ; and an MES of $\leq 1$ without friability.
Clinical response	Determined using the mMCS: Decrease from baseline in the mMCS $\geq 2$ points and $\geq 30\%$ from baseline, plus a decrease in rectal bleeding subscore $\geq 1$ or an absolute rectal bleeding subscore $\leq 1$
MCS remission	MCS $\leq 2$ and no subscore higher than 1
MCS response	Decrease in MCS $\geq 3$ points and $\geq 30\%$ from baseline, plus a decrease in rectal bleeding score $\geq 1$ or an absolute rectal bleeding score $\leq 1$
Histologic remission by RHI	RHI $\leq 3$ (with 0 for lamina propria neutrophils score and neutrophils in the epithelium score and without ulcers or erosions)
Histologic remission by NI	NI=0
Histologic remission by Continuous Geboes	Continuous Geboes $\leq 3$
Histologic improvement	$\geq 7$ -point reduction in RHI
Endoscopic improvement	MES $\leq 1$
Endoscopic remission	MES=0
Mucosal healing	MES=0 and RHI $\leq 3$ (with 0 for lamina propria neutrophils score and neutrophils in the epithelium score and without ulcers or erosions)
Mucosal improvement	MES $\leq 1$ and $\geq 7$ -point reduction in RHI
Symptomatic response	Decrease in Partial mMCS $\geq 1$ point and $\geq 30\%$ from baseline, plus a decrease in rectal bleeding subscore $\geq 1$ or an absolute rectal bleeding subscore $\leq 1$
Partial MCS response	Decrease in Partial MCS $\geq 2$ points and $\geq 30\%$ from baseline, plus a decrease in rectal bleeding subscore $\geq 1$ or an absolute rectal bleeding subscore $\leq 1$

Term	Definition
Time to symptomatic response	Time from randomization date to symptomatic response
Corticosteroid-free remission	Determined only in participants who were receiving corticosteroids on study Day 1. Includes such participants who are both in clinical remission (as determined using the mMCS) at Week 52 and off corticosteroids for $\geq 8$ consecutive weeks prior to Week 52.

Please see details of efficacy assessments in Section 6.3 of this document and Section 8.7 of the study protocol.

## 1.2. Study Design

This study is a randomized, double-blind, placebo controlled, multicenter, Phase 2b study to evaluate the efficacy and safety of 3 active dose regimens of MORF-057 (as capsule, P.O.) versus matching placebo in study participants with moderately to severely active UC.

Approximately 280 participants will be randomized into the treatment groups in a 1:1:1:1 ratio (i.e., 70 participants per group). The study will enroll participants who are advanced therapy naïve (i.e., have no previous exposure to an advanced therapy treatment for UC) and advanced therapy experienced (excluding vedolizumab), with at least 30% but no more than 40% of advanced therapy experienced participants. Randomization stratification factors will include baseline MES (<3 vs 3) and previous use of advanced therapy treatment (advanced therapy naïve vs advanced therapy experienced). All participants will be enrolled from approximately 150 centers worldwide. For this study, moderately to severely active UC will be defined as having an mMCS of 5 to 9 (inclusive), with an MES  $\geq 2$  (confirmed by central reader).

The main part of this Phase 2b study will consist of a Screening Period (up to 6 weeks, consisting of Stage 1 and Stage 2 testing), a Treatment Period (52 weeks, including a 12-week Induction Period and a 40-week Maintenance Period), and a Safety Follow up (SFU) Period (4 weeks).

During the main part of this study, there will be approximately 11 scheduled study visits: Screening Visit(s) (Visit 1 at Weeks 6 to 1), multiple Treatment Visits (Visits 2-10 at Weeks 0, 2, 6, 12, 18, 24, 32, 42, and 52 [End of Treatment (EOT)]), and an SFU Visit (visit to occur 4 weeks after the last dose of study drug is received, which will be at Week 56 if the full Treatment Period is completed or earlier if treatment is discontinued early). Study Day 1 represents the first day of the Treatment Period (i.e., when the participant will receive the first dose of study drug).

All participants who complete the 52-week Treatment Period will have the opportunity to continue their treatment in a 52-week Maintenance Extension Period.

During the optional Maintenance Extension, there will be 5 scheduled visits: 4 Treatment Visits (Visits 11-14 at Weeks 65, 78, 91, and 104 [EOT]) and an SFU Visit (visit to occur 4 weeks after the last dose of study drug is received, which will be at Week 108 if the full Maintenance Extension is completed or earlier if treatment is discontinued early).

Participants who do not enroll into the Maintenance Extension must complete the final SFU Period for the main part of the study, including the Week 56 Visit (4 weeks after receiving the last dose of MORF-057), for a maximum time on study of 62 weeks. Participants who choose to continue in the Maintenance Extension will not complete the SFU Period for the main part of the study; instead, they

Morphic Therapeutic, Inc.  
Study Number: MORF-057-202

Statistical Analysis Plan  
Version 1.0, 16SEP2024

will directly enter the Maintenance Extension and complete a separate SFU Period, including the Week 108 Visit (4 weeks after receiving the last dose of MORF-057), for a maximum time on-study of 114 weeks.

An independent Data and Safety Monitoring Board (DSMB) will review participant safety data and monitor scientific integrity throughout the study. Details related to the DSMB will be clearly delineated in the DSMB Charter.

[figure not shown]
Enrolled participants will be randomized to a treatment group to receive active MORF-057 or placebo. Participants initially randomized into an active MORF-057 treatment group will receive an active treatment (according to study period and group assignment) for the full 52-week Treatment Period. Participants initially randomized into the placebo group will be switched to an active MORF-057 regimen (200 mg once a day – evening [Q.D.E]) after they complete the Induction Period and the Week 12 assessments. After participants complete the full 52-week Treatment Period, they will have the option to enter an additional 52-week Maintenance Extension Period. All participants who choose to continue in the Maintenance Extension will continue receiving the same MORF-057 regimen they had during the Maintenance Period for up to an additional 52 weeks. The dosing regimens for the 4 treatment groups during the study are shown below.

**Table 3: Study Dose Regimens**

	Induction Period (12 Weeks)	Maintenance Period (40 Weeks)/ Maintenance Extension Period (52 Weeks)
Group 1	MORF 057 (200 mg B.I.D.)	MORF 057 (100 mg B.I.D.)
Group 2	MORF 057 (100 mg B.I.D.)	MORF 057 (100 mg B.I.D.)
Group 3	MORF 057 (100 mg Q.D. M)	MORF 057 (100 mg Q.D. M)
Group 4	Placebo	MORF 057 (200 mg Q.D. E)

B.I.D.: twice a day; Q.D. E: once a day (evening); Q.D. M: once a day (morning).

A study schema is provided in [Figure 1](#).

**Figure 1: Study Schema**

B.I.D.: twice a day; EOT: End of Treatment; Q.D. E: once a day (evening); Q.D. M: once a day (morning); SFU: Safety Follow up; UC: ulcerative colitis; V: visit; W: week.

\* The SFU Visit at Week 56 will not be performed for participants who enter the Maintenance Extension Period.

† The assessments to be performed at each visit and the acceptable time windows for each visit are provided in the Schedule of Activities.

‡ In cases where the participant withdraws early from the study treatment, the EOT and SFU Visit assessments may be performed earlier than the timepoints shown here.

A participant is considered to have completed the study if he/she has completed the Screening and 52-week Treatment Periods of the main part of the study and attended the SFU Visit OR has completed the Week 52/EOT Visit and has been enrolled into the Maintenance Extension Period.

The end of the study is defined as the date of the last visit of the last participant in the main part of the study or last scheduled procedure shown in the Schedule of Activities (SoA) for the last participant in the main part of the study globally.

### 1.3. Sample Size and Power

The sample size was determined based on the primary endpoint of clinical remission at Week 12 by using the Chi-Squared Test to compare two proportions. A sample size of 70 participants per group (giving a total of 280) will provide 80% power to detect a difference of 15% in the clinical remission rate between MORF-057 and placebo, based on the use of a two-sided test at the alpha=0.10 level of significance. The calculation is based upon an assumed placebo remission rate of 7%.

### 1.4. Randomization and Blinding

#### 1.4.1. Randomization

An interactive response technology (IRT) will be used to centrally randomize all participants into 1 of the 4 treatment groups (see [Table 3](#) for dosing regimens). The randomization code will be maintained by the IRT provider. Randomization will be stratified by baseline MES (<3 vs 3) and previous use of advanced therapy treatment (advanced therapy naïve vs advanced therapy experienced). Participants

Morphic Therapeutic, Inc.  
Study Number: MORF-057-202

Statistical Analysis Plan  
Version 1.0, 16SEP2024

initially randomized into the placebo group will be switched to an active MORF 057 regimen (200 mg Q.D. E) after they complete the Induction Period and the scheduled assessments at Week 12 (including endoscopy).

Study treatment will be dispensed at the study visits as summarized in the Schedule of Activities (SoA) in Section 1.2 of the study protocol.

#### **1.4.2. Blinding**

This is a double-blind study in which the Sponsor, participants, site staff, site pharmacy, Investigators, and outcome assessors will be blinded to the study treatment through Week 12. The double-blind will be maintained by using identical study drug bottles and labels for MORF-057 and placebo. The placebo will have an identical appearance to that of the MORF-057 capsules. Participants will receive their study drug supplies in “morning bottles” and “evening bottles.” Each participant will receive the same number of “morning bottles” and “evening bottles” according to the respective study period (Induction or Maintenance/Maintenance Extension). In the morning, participants should take 1 capsule from EACH “morning bottle.” In the evening, participants should take 1 capsule from EACH “evening bottle.” After all participants have completed the Induction Period and scheduled assessments at the Week 12 Visit, the Induction Period analyses will be performed. After the database lock for the Induction Period analyses, the analysis results will be unblinded at the population level. However, the access to treatment assignment for individual participants will be limited to only the necessary persons from the Sponsor and the external vendors that will generate the unblinded analysis results and perform the validation. All other Sponsor personnel, the project study team, site Investigator, site staff, and study participants will remain blinded to the individual treatment assignments through the end of the study. The details of measures taken to maintain integrity of blinded data was described in the study blinding plan.

The IRT will be programmed with blind breaking instructions. In case of an emergency, the Investigator has the sole responsibility for determining if unblinding a participant’s treatment assignment is warranted. Participant safety must always be the first consideration in making such a determination. If the Investigator decides that unblinding is warranted, the Investigator should make every effort to contact the Sponsor prior to unblinding a participant’s treatment assignment, unless this could delay emergency treatment for the participant. If a participant’s treatment assignment is unblinded, the Sponsor must be notified within 24 hours of this occurrence. The date and reason for the unblinding must be recorded in the participant’s medical records and IRT. If a participant’s treatment is unblinded, the participant will be withdrawn from the study.

Sponsor safety staff or designee may unblind the treatment assignment for any participant in case the SAE meets the requirement for expedited reporting (e.g., is a suspected unexpected serious adverse reaction [SUSAR]). If the report requires expedited reporting to one or more regulatory agencies, a copy of the report, identifying the participant’s treatment assignment, will be sent to the regulatory agency in accordance with local regulations and/or Sponsor policy. All other Sponsor staff, as well as the Investigators and study participants, will remain blinded to study assignments until database lock.

#### **1.5. Planned Analysis**

The Treatment Period (i.e., 52 weeks) in the main part of the study includes the 12-week Induction Period and the 40-week Maintenance Period, see Section 1.2. The Induction Period includes the placebo group as a comparator, while all the participants will receive an active MORF-057 treatment during the Maintenance Period. For the purpose of statistical analyses, the Induction Period and the Maintenance

Period will be treated as 2 independent parts. There will be 2 analyses planned for the main part of the study: one for the 12-week Induction Period (i.e., the period for the primary efficacy endpoint) and one for the 52-week Treatment Period (i.e., the 12-week Induction Period plus the 40-week Maintenance Period).

Additionally, at the end of the optional Extension Period, another analysis will be performed for the 104-week Total Treatment Period, which includes the main part of the study and the 52-week Maintenance extension period.

### **1.5.1. Induction Period Analysis**

The Induction Period Analysis will be performed after all the participants have completed the Week 12 assessments or discontinued the study before the Week 12 assessments. The analysis will formally evaluate the primary and secondary efficacy endpoints, all the exploratory efficacy endpoints defined by Week 12, and safety of MORF057 vs placebo during the 12-week Induction Period. The PK and PD data during the 12-week Induction Period will also be summarized.

The 12-week Induction Period is defined as the time from the date of randomization to the Induction Period Last Dose date recorded on the Study Period Transition electronic case report form (eCRF) for participants continuing to the Maintenance Period, or the study end date (i.e., the date of the last visit including the SFU visit or last scheduled procedure) for participants who have discontinued the study before entering the Maintenance Period.

If participants continue to the Maintenance Period, they should complete all the Visit 5 (Week 12) assessments before starting their maintenance treatment according to the protocol. However, a small number of participants were observed to deviate from the protocol by starting their maintenance treatment shortly before completing all the Visit 5 (Week 12) assessments. In such cases, all efficacy assessments, clinical laboratory tests, vital signs and electrocardiogram (ECG) collected at Visit 5 (Week 12) will still be included in the analyses for the 12-week Induction Period, even if they are measured after the participants start their maintenance dose. The PK and PD samples collected at Visit 5 (Week 12) for these participants will be handled in the Induction Period Analysis according to the rules specified in Section 2.7 and Section 2.8. Any adverse events that occur after the date of last induction treatment dose will not be included in the Induction Period Analysis. If both the last induction treatment dose and the first maintenance treatment dose occur on the same day, any adverse events reported on that day will be considered for the Maintenance Period and not included in the Induction Period Analysis, unless there is evidence to confirm that the events occurred before the administration of the maintenance treatment.

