## 2.8. Handling Rules for PD Data

For  $\alpha 4\beta 7$  and  $\alpha 4\beta 1$  receptor occupancies, and relative CCR9 mRNA expression which are collected at Visit 5 (Week 12),

- If participants are randomized into Group 2 (MORF-057 100 mg B.I.D. – MORF-057 100 mg B.I.D) or Group 3 (MORF-057 100 mg Q.D.-M – MORF-057 100 mg Q.D.-M), all data collected at Visit 5 (Week 12) will be considered as valid and included in the table summary for the Induction Period analysis.
- If participants are randomized to Group 1 (MORF-057 200 mg B.I.D. – MORF-057 100 mg B.I.D.) or Group 4 (Placebo – MORF-057 200 mg Q.D.-E), any data collected after the first maintenance dose will be considered as invalid and not be included in the table summary but provided in the listings.

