## 4.8. Efficacy Analysis

Unless otherwise specified, all efficacy endpoints will be analyzed based on the FAS.

In the analyses stratified by the randomization stratification factors (baseline MES [ $<3$  vs  $3$ ] and previous use of advanced therapy treatment [advanced therapy-naïve vs advanced therapy-experienced]), any participant who was randomized under the wrong stratum by mistake will be analyzed according to the actual stratum the participant belongs to, unless otherwise specified.

The 12-week Induction Period Analysis will include the primary efficacy endpoint, secondary efficacy endpoint, and all exploratory efficacy endpoint defined by Week 12, comparing MORF-057 versus placebo. As specified in Section 1.5, if participants start their maintenance treatment before completing the efficacy assessment at Visit 5 (Week 12) due to a protocol deviation, the efficacy data collected at Visit 5 (Week 12) will still be included in the analyses for the 12-week Induction Period, even if they are measured after the participants start their maintenance dose..

The 52-week Treatment Period Analysis will include all exploratory efficacy endpoints defined at Week 52, and the 104-week Total Treatment Period Analysis will include all exploratory efficacy endpoints defined at Week 104. All those exploratory endpoints will be summarized descriptively by treatment groups.

In the analyses for the 52-week Treatment Period and the 104-week Total Treatment Period, for participants randomized to the treatment group with placebo as the induction treatment and MORF-057 200 mg Q.D.-E as the maintenance treatment, they will be presented in the treatment group denoted by 200mg Q.D.-E. Summaries for this group will be based on the participants randomized to the placebo group during the Induction Period who have subsequently continued to the Maintenance Period. The denominator for calculating the proportions for this group will be the number of participants continuing to the Maintenance Period, unless otherwise specified. In all by-visit summaries and plots, only visits after Visit 5 (Week 12) will be presented for this group.

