**Figure 2: Hierarchical Testing Procedure**

## 4.9. Safety Analysis

All safety analyses will be performed based on the safety data collected during the on-treatment period, which is defined as the period from the administration of the first dose of study drug up to 7 days after the last dose of study drug, unless specified otherwise. The safety data will be summarized by treatment groups and the pooled MORF-057 groups based on the Safety Population defined in Section 3.3.

The safety analysis for the Induction Period will include the safety data collected during the 12-week Induction Period (see Section 1.5.1). If participants start their maintenance treatment before completing all safety assessments at Visit 5 (Week 12) due to a protocol deviation, clinical laboratory tests, vital signs and ECG at Week 12 visit will still be included in the 12-week Induction Period Analysis, even if they are measured after the participants start their maintenance dose.

The safety analysis for the 52-week Treatment Period will include cumulative safety data collected during the entire 52-week Treatment Period for the treatment groups randomized to an active MORF-057 dose. For the treatment group initially randomized to placebo and subsequently switched to an

Morphic Therapeutic, Inc.  
Study Number: MORF-057-202

Statistical Analysis Plan  
Version 1.0, 16SEP2024

active MORF-057 dose for maintenance treatment, only safety data collected during the 40-week Maintenance Period will be included for the participants in this group who have continued to the Maintenance Period and received MORF-057, as described in Section 1.5.2.

The safety analysis for the 104-week Total Treatment Period will include cumulative safety data collected during the entire 104-week Total Treatment Period for the treatment groups initially randomized to an active MORF-057 dose. For the treatment group initially randomized to placebo and subsequently switched to an active MORF-057 dose for maintenance treatment, only safety data collected during the 40-week Maintenance and 52-week Extension Periods will be included for the participants in this group who have continued to the Maintenance Period and received MORF-057, as described in Section 1.5.3.

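### Group 4 laboratory, vital-sign and ECG values taken at Week 12 after the first MORF-057 dose are tabulated under placebo, while adverse events from the same time go to 200 mg Q.D.-E

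*SAP*

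**What the plan says.** Section 1.5.1 ends the Induction Period, for participants who continue, at the last induction dose recorded on the Study Period Transition eCRF. It then makes an exception for those who started maintenance shortly before finishing Visit 5: their efficacy, laboratory, vital-sign and ECG results "will still be included in the analyses for the 12-week Induction Period, even if they are measured after the participants start their maintenance dose". Section 4.8 repeats this for efficacy ("the efficacy data collected at Visit 5 (Week 12) will still be included in the analyses for the 12-week Induction Period") and Section 4.9 for safety ("clinical laboratory tests, vital signs and ECG at Week 12 visit will still be included in the 12-week Induction Period Analysis").

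Other data from the same days are treated differently:

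- **Adverse events.** "Any adverse events that occur after the date of last induction treatment dose will not be included in the Induction Period Analysis" (Section 1.5.1). If the last induction and first maintenance doses share a date, then unless there is evidence of earlier onset, "any adverse events reported on that day will be considered for the Maintenance Period and not included in the Induction Period Analysis". Section 4.9.1 shows such events for placebo switchers under 200 mg Q.D.-E.
- **PD.** For Groups 1 and 4, "any data collected after the first maintenance dose will be considered as invalid and not be included in the table summary" (Section 2.8). For Groups 2 and 3, whose regimen does not change, "all data collected at Visit 5 (Week 12) will be considered as valid and included in the table summary for the Induction Period analysis".
- **PK.** For Group 1, samples after the first maintenance dose are invalid (Section 2.7.2).

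Table 8 gives the content of the Group 4 maintenance kit: the morning capsule is placebo and both evening capsules are MORF-057.

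**The concern.** The SAP already recognises, for adverse events and PD, that crossing into maintenance changes what a Group 4 observation represents. For laboratory tests, vital signs and ECG it ignores the crossing. Once a Group 4 participant has taken an evening maintenance dose, an abnormal laboratory value at Visit 5 is tabulated under placebo, and the adverse event reported for it is tabulated under 200 mg Q.D.-E.

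Induction is the only period with a placebo comparator (Section 1.5), so its by-visit and worst-value safety tables are the controlled safety evidence. On-drug values in the placebo column can dilute or misplace a difference there. Laboratory and adverse-event tables for one participant would also disagree about the treatment received.

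The efficacy rule raises the same question for Groups 1 and 4, but less forcefully, because efficacy is analysed by randomized arm.

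**Working it through.** **1. Group 4 data obtained after the first evening maintenance dose, rule by rule**

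| Data | Where the SAP puts it | Section |
|---|---|---|
| Laboratory, vital signs, ECG | Placebo, Induction | 1.5.1, 4.9 |
| Efficacy | Placebo, Induction | 1.5.1, 4.8 |
| Adverse events | 200 mg Q.D.-E | 1.5.1, 4.9.1 |
| Receptor occupancy, CCR9 mRNA | Listed only, invalid | 2.8 |
| Use as 52-week safety baseline | Not allowed (too late) | 2.1.1 |

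The first row disagrees with the third and fourth, and also with the dated end of the Induction Period in 1.5.1.

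**2. Does another rule correct it?** The actual-treatment rule in Section 3.3 covers placebo participants who receive MORF-057 by mistake during the Induction Period. For continuing participants that period ends at the last induction dose, so early maintenance dosing lies outside it and the values are not moved.

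**3. Which values are on drug?** The Group 4 morning maintenance capsule is placebo. A participant who took only that capsule before the assessments had received no MORF-057. The relevant cut is therefore the first evening maintenance dose.

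**4. Size for safety.** The planned group size is 70 (Section 1.3). The number of affected placebo participants, k, is not given, so take k = 1 to 5 as an assumed range.

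- Share of the placebo Week 12 row that is post-switch = k/70: 1/70 = 1.4%, 2/70 = 2.9%, 5/70 = 7.1%.
- A placebo mean moves by (k/70) × any drug effect on that parameter. In a shift table each such participant is worth 1.4 percentage points.

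**5. Size for efficacy.** First the plan's own figure. With n = 70, 7% versus 22% and two-sided alpha 0.10 (z = 1.645), the pooled rate is 0.145.

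- Null standard error = √(2 × 0.145 × 0.855/70) = 0.0595.
- Alternative standard error = √((0.07 × 0.93 + 0.22 × 0.78)/70) = 0.0581.
- Power = Φ((0.15 − 1.645 × 0.0595)/0.0581) = 81.5%, against the stated 80%. It reproduces.

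Now suppose each switched placebo participant already had the active rate, an implausible bound so soon after switching. The placebo rate becomes 0.07 + (k/70) × 0.15.

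- k = 1: placebo 7.2%, difference 14.8 points, power 80.3%.
- k = 5: placebo 8.1%, difference 13.9 points, power 75.0%.

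The distortion works against MORF-057.

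**6. Which sensitivity analysis?** Setting the affected assessments to missing under NRI turns affected placebo remitters into nonresponders. With k = 5 in placebo only, the expected placebo rate falls to 0.07 × 65/70 = 6.5% and the difference rises to 15.5 points, in favour of the drug. Excluding the affected participants avoids this.

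**The case against.** The best defence is that the rule is openly prespecified and answers a deviation described as rare and close to the visit. Several parts of it stand.

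- **Timing.** A maintenance dose is not always a MORF-057 dose in Group 4. A cut at any first maintenance dose would discard genuine placebo values.
- **Cause.** A value drawn shortly after a first active dose may still mainly reflect the preceding 12 weeks.
- **Efficacy.** The FAS follows the randomized arm (Section 3.1). Contamination of placebo shrinks the difference. Diary subscores use days within 7 days of a reference date set at the earliest of visit, bowel preparation and endoscopy (Section 6.1), so they largely predate a short overlap. The PP analysis can remove these cases, though only if the deviation is classed as major, and Table 4 does not apply PP to safety.
- **Count.** If the deviation were spread evenly over four groups, 5 in placebo would mean about 20 in the trial, which is hard to call small. The true k may be 0 or 1.

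Two stronger readings are tempting. A reader might infer that the rule conceals a safety signal. The documents do not support that: only Week 12 values and the Induction worst value can be affected, adverse events remain visible under 200 mg Q.D.-E, all laboratory, vital-sign and ECG data are listed, and combined liver-test elevations have their own listing (Section 4.9.2). A reader might also infer that values are counted twice. Section 4 removes Visit 5 from Group 4's 52-week and 104-week by-visit tables. An appearance in the later worst-value summary would be correct attribution in a separate analysis, not a second count in one table.

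None of this explains why safety measurements and adverse events from the same hours belong to different treatments.

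**Conclusion.** The inconsistency is real and confined. It concerns Group 4 laboratory, vital-sign and ECG values taken at Visit 5 after the first MORF-057-containing maintenance dose, which are reported as placebo against the SAP's own period definition and its adverse-event and PD rules. In Group 1 the corresponding safety values remain on MORF-057 at a different dose, so no value on drug is shown as placebo.

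The effect is probably minor: 1.4% to 7.1% of placebo Week 12 values for an assumed 1 to 5 affected of 70, and nothing if every affected participant had taken only the morning capsule. The as-randomized efficacy rule is defensible and, for Group 4, conservative if anything. It lacks only a dedicated check. The point is worth settling because it touches the only placebo-controlled safety tables and is cheap to correct.

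**What to change.** - **Sections 1.5.1 and 4.9.** Leave Group 4 laboratory, vital-sign and ECG values taken after the first MORF-057-containing maintenance dose out of the Induction placebo summaries, including the worst-value shift tables. Flag them in the listings. State that they may enter only the 200 mg Q.D.-E worst-value summaries, since Section 4 already excludes Visit 5 from that group's later by-visit tables. Say how values on the same date as that dose are resolved when no time is recorded.
- **Sections 4.8.1.2 and 4.8.2.** Keep the as-randomized FAS analysis. Add one sensitivity analysis that excludes Group 1 and Group 4 participants whose Week 12 assessments followed the regimen change. Do not use a treat-as-missing run under NRI, for the reason shown in step 6 of the working.
- **Reporting.** Give the number affected and the gap between first maintenance dose and assessment, by arm.

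The cost is SAP wording, a comparison of dates largely needed already for the PD rule, and one extra table. A few Week 12 safety values drop out of the Group 4 Induction summaries and appear in no by-visit table, which leaves slightly more missing data in that arm than in the others. They remain in the listings.
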